## SOA Footnotes

Treatment cycles are 28 days (4 weeks). Patients may continue treatment with AC176 as long as they are deriving clinical benefit according to the Investigator's judgment.

- a Pre-screening if applicable and screening procedures are described in [Table 1](#). Written ICF for the main study must have been obtained before undertaking any study-related procedures and prior to the initiation of study treatment.
- b Physical examinations including the measurements of height (screening only) and weight will be done at screening, Cycle 1 Day 1, Cycle 1 Day 15, on Day 1 of each subsequent treatment cycle, at the end-of-treatment (EOT) visit, and at the 30-day safety follow-up (FU) visit. ECOG performance status will be done at screening and at all subsequent visits.
- c The following screening parameters should be done  $\leq 14$  days prior to first dose of study drug administration: physical examination (including height and weight), Eastern Cooperative Oncology Group (ECOG) performance status, triplicate electrocardiograms (ECGs), vital signs, hematology (including absolute lymphocyte count, absolute neutrophil count, red blood cell count, reticulocytes, hemoglobin, hematocrit, platelet counts, prothrombin time/partial thromboplastin time (or aPTT [activated/PTT])/international normalized ratio [PT/PTT/INR]), biochemistry (sodium, potassium, phosphate, chloride, creatinine, total calcium, venous bicarbonate [ $HCO_3$ ], albumin, total protein, aspartate aminotransferase [AST], alanine aminotransferase [ALT], alkaline phosphatase [ALP], total bilirubin, lactate dehydrogenase, glucose, creatine kinase [CK-if CK is elevated, and if it is clinically significant at the PI's discretion], then CK-MB, troponin I, and myoglobin should be reactively tested, with further follow-up as clinically warranted], urea nitrogen, and uric acid), and urinalysis. Vital signs (blood pressure, body temperature, pulse rate, and respiration rate) are checked at every visit prior to blood work and administration of treatment at the discretion of the Investigator. Safety laboratory assessments including hematology, biochemistry, coagulation and urinalysis will be performed locally. On Cycle 1 Day 8, the CBC may be performed by local laboratory as long as it can be entered into the eCRF and is approved by the Investigator. If some examinations cannot be completed at the study site, corresponding examinations should be used in replacement (e.g.,  $CO_2$  vs  $HCO_3$ ), and this does not need to be reported as a protocol deviation.
- d Immature platelet fraction (IPF) testing will be evaluated when a patient experiences platelet count decrease, or anytime at the discretion of the physician and if the test can be run at the site. CBCs should be collected at the same time as the IPF collection. IPF is not required at screening.
- e Triplicate 12-lead ECGs will be done at screening ( $\leq 14$  days prior to first dose), before treatment on Cycle 1 Day 1 and Cycle 1 Day 15; before treatment on Day 1 of each subsequent cycle, at the EOT, and at any other time the Investigator deems it necessary. ECGs should be assessed before the patient takes the study drug that day, before other procedures, and after the patient has rested for at least 3 minutes. Each recording should be separated by at least 30 seconds.
- f Additional triplicate ECGs will be performed on Cycle 1 Day 1 and Day 15 just before the 2 hour and 4 hour post-dose PK blood samples are collected. Refer to [Appendix G](#) for additional ECG collections required during PK blood collections.
- g Pharmacokinetic (PK) sampling will be based on dosing schedule (see [Appendix G](#), [Table 9](#), [Table 11](#), [Table 10](#)):
  1. 7 days on and 7 days off (Table 9): Pharmacokinetic(PK) sampling will be collected on Cycle 1 Day 1 and 8 pre-dose and post-dose at: 1 and 2 hours ( $\pm 5$  minutes), 3 and 4 hours ( $\pm 10$  minutes), 6 ( $\pm 20$  minutes), and 8 hours, 10 and 12 hours ( $\pm 1$  hour), and 24-hours post dose ( $\pm 1$  hour). In addition to the pre-dose ECGs collected on Cycle 1 Day 1 and 8, triplicate ECGs will also be obtained on Cycle 1 Day 1 and 8 just before the 4-hour and 8-hour post-dose PK blood samples are collected. On Cycle 2 Day 8, Cycle 4 Day 8, and Cycle 6 Day 8, a pre-dose PK sample will be collected from all patients. Triplicate ECGs will be obtained before the pre-dose PK collection on Day 8 of Cycle 2, Cycle 4, and Cycle 6.
  2. 5 days on and 2 days off (Table 11): Pharmacokinetic (PK) sampling will be collected on Cycle 1 Day 1 and 5 pre-dose and post-dose at: 1 and 2 hours ( $\pm 5$  minutes), 3 and 4 hours ( $\pm 10$  minutes), 6 ( $\pm 20$  minutes), 8, 10 and 12 hours ( $\pm 1$  hour), and 24-hours post dose ( $\pm 1$  hour). In addition to the pre-dose ECGs collected on Cycle 1 Day 1 and 5, triplicate ECGs will also be obtained on Cycle 1 Day 1 and 5 just before the 4-hour and 8-hour post-dose PK blood samples are collected. On Cycle 1 Day 8, Cycle 2 Day 6, Cycle 4 Day 6, and Cycle 6 Day 6, a pre-dose PK sample will be collected from all patients. Triplicate ECGs will be obtained before the pre-dose PK collection on Day 6 of Cycle 2, Cycle 4, and Cycle 6.
  3. 4 days on and 3 days off (Table 10): pharmacokinetic (PK) sampling will be collected on Cycle 1 Day 1 and 4 pre-dose and post-dose at: 1 and 2 hours ( $\pm 5$  minutes), 3 and 4 hours ( $\pm 10$  minutes), 6 ( $\pm 20$  minutes), 8, 10 and 12 hours ( $\pm 1$  hour), and 24-hours post dose ( $\pm 1$  hour). In addition to the pre-dose ECGs collected on Cycle 1 Day 1 and 4, triplicate ECGs will also be obtained on Cycle 1 Day 1 and 4 just before the 4-hour and 8-hour post-dose PK blood samples are collected. On Cycle 1 Day 8, Cycle 2 Day 5, Cycle 4 Day 5, and Cycle 6 Day 5, a pre-dose PK sample will be collected from all patients. Triplicate ECGs will be obtained before the pre-dose PK collection on Day 5 of Cycle 2, Cycle 4, and Cycle 6.

If the sample cannot be collected at the visit as scheduled, it should be collected at the next visit whenever possible. Additional unscheduled PK samples may be drawn during the study if it is deemed clinically indicated for the patient and/or based on newly emerged data from clinical studies of AC176. Meal consumption prior to PK collection will

CONFIDENTIAL

Study Drug: AC176

Sponsor/Development Innovations Study Number: AC176-001/GU 207

Final Protocol: 10 July 2023 Version 4.0

be collected. The last meal consumed prior to dosing on the day of full PK collections during Cycle 1 should be recorded. The visit days and sampling time points are outlined in [Appendix G](#).

h Expansion Cohort (Part B) PKs sample collections are different from Part A cohort collections.

1. For 7 days on and 7 days off: The Expansion Cohort PKs are collected pre-dose on Cycle 2 Day 8, Cycle 4 Day 8, and Cycle 6 Day 8. Triplicate ECGs will be obtained before the pre-dose PK collection on Day 8 of Cycle 2.
2. For 5 days on and 2 days off dosing schedule: the Expansion Cohort PKs are collected on Day 6 of Cycle 2, 4, and 6. Triplicate ECGs will be obtained before the pre-dose PK collection on Day 6 of Cycle 2.
3. For 4 days on and 3 days off dosing schedule: the Expansion Cohort PKs are collected on Day 5 of Cycle 2, 4, and 6. Triplicate ECGs will be obtained before the pre-dose PK collection on Day 5 of Cycle 2.

Additional unscheduled PK samples may be drawn during the study if it is deemed clinically indicated for the patient and/or based on newly emerged data from clinical studies of AC176. The visit days and sampling time points are outlined in [Appendix G](#).

i Fresh tumor biopsies on treatment are optional. If patient agrees to an on-treatment biopsies, the biopsy will be taken on Cycle 2 Day 1 (+ 5 days) (see Section [7.8.1](#)).

j All patients will retrospectively undergo central laboratory testing for AR mutation confirmation at C1D1. Blood samples for ctDNA will be collected prior to dosing at predose Cycle 1 Day 1, and on Cycle 2 Day 1, Cycle 5 Day 1, and Cycle 8 Day 1, and at EOT as outlined in Section [7.8.2](#).

k Blood samples for ARv7 testing will be collected prior to dosing at Cycle 1 Day 1 and at EOT as outlined in Section [7.8.2](#).

l Patients dosing schedule may include:

1. 7 days on and 7 days off, e.g., C1D1 to C1D7 receive AC176. Dose interrupted C1D8 to C1D14. AC176 dose to continue Cycle 1 on C1D15 to C1D21 and interrupted C1D22 to C1D28. From Cycle 2, the patients will be dosed for 7 days and interrupted 7 days.
2. Patients will be dosed 5 days on and 2 days off, e.g., C1D1 to C1D5 receive AC176. Dose interrupted C1D6 to C1D7. AC176 dosed to continue Cycle 1 on C1D8 to C1D12 and interrupted C1D13 to C1D14. C1D15 to C1D19 receive AC176. Dose interrupted C1D20 to C1D21. AC176 dosed to continue Cycle 1 on C1D22 to C1D26 and interrupted C1D27 to C1D28.
3. Patients will be dosed one week 4 days on and one week 3 days off, e.g., C1D1 to C1D4 receive AC176. Dose interrupted C1D5 to C1D7. AC176 dosed to continue Cycle 1 on C1D8 to C1D11 and interrupted C1D12 to C1D14. C1D15 to C1D18 receive AC176. Dose interrupted C1D19 to C1D21. AC176 dosed to continue Cycle 1 on C1D22 to C1D25 and interrupted C1D26 to C1D28.

Patients will be instructed to take one dose of AC176 at the same time every day immediately after a meal. The patients will be asked to take AC176 in the morning immediately after a meal, and other concomitant medications in the evening; or at least 4 hours apart from taking AC176, if possible. Study drug compliance will be assessed at each patient visit by review of the dosing diary.

m Prostate-specific antigen (PSA) blood samples will be taken  $\leq$ 4 weeks prior to initiation of treatment, prior to dosing Cycle 1 Day 1 (unless collected within the previous 72 hours), and at Day 1 of every cycle, and at the EOT visit if not taken in the previous 4 weeks, and at progression. Additional PSA assessments after the 30-day safety follow-up visit will be performed as on treatment until PD or another withdrawal criterion is met.

n CT/MRI scans of the chest, abdomen and pelvis should be taken  $\leq$ 4 weeks prior to initiation of treatment. CT/MRI scans of the chest, abdomen, and pelvis should be taken every 2 cycles (8 weeks)  $\pm$ 5 days up to 24 weeks, then every 12 weeks  $\pm$ 5 days, and at the End of Study visit (if scans were not taken in the previous 8 weeks) and, if clinically indicated, imaging of any other known or suspected sites of disease (e.g., brain). Lymph nodes should be evaluated using PCWG3 criteria and not RECIST v1.1.

o Bone scans - technetium only -  $\leq$ 4 weeks prior to initiation of treatment, every 2 cycles (8 weeks)  $\pm$ 5 days up to 6 cycles (24 weeks), then every 3 cycles (12 weeks)  $\pm$ 5 days, and at the End of Study visit if scans were not taken in the previous 8 weeks. Bone lesions should be evaluated using PCWG3 criteria and not RECIST v1.1.

p An EOT visit should be performed for all patients who permanently discontinue study treatment. If the decision to permanently discontinue treatment is made at a scheduled visit, the EOT visit should be performed instead of the scheduled visit (preferably within 7 days and no later than 14 days after the last treatment).

q All patients will be followed during the off-treatment period until all treatment-related toxicity resolves, or for at least 30 days post-study drug discontinuation, or until the start of another anti-cancer treatment. Any concomitant medications received up to 30 days after the last dose of study medication should be recorded.

r Follow-up for PD visits for tumor assessment by imaging (CT scan/MRI/bone scan, if applicable) for patients who discontinue study treatment without having PD based on RECIST v1.1 (see [Appendix B](#)) should be performed as on treatment until PD or another withdrawal criterion is met (see Section [7.5.3](#)). At these visits, serious adverse events (SAEs) occurring during the study that are considered to be related to study treatment or procedures will be followed until resolution.

CONFIDENTIAL

Study Drug: AC176

Sponsor/Development Innovations Study Number: AC176-001/GU 207

Final Protocol: 10 July 2023 Version 4.0

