## Appendix G: PK Sampling Timepoint Schedules

**Table 8 PK Sampling Timepoints Once Daily (QD Dosing)**

	Timepoints relative to AC176 dosing*	ECG* (in triplicate)
Cycle 1 Day 1	Pre-dose	X
	1 hour ( $\pm 5$ minutes)	-
	2 hour ( $\pm 5$ minutes)	-
	3 hour ( $\pm 10$ minutes)	-
	4 hour ( $\pm 10$ minutes)	X
	6 hour ( $\pm 20$ minutes)	-
	8 hour ( $\pm 1$ hour)	X (if feasible)
	10 hour ( $\pm 1$ hour)	-
	12 hour ( $\pm 1$ hour)	-
	24 hour ( $\pm 1$ hour)	-
Cycle 1 Day 15	Pre-dose	X
	1 hour ( $\pm 5$ minutes)	-
	2 hour ( $\pm 5$ minutes)	-
	3 hour ( $\pm 10$ minutes)	-
	4 hour ( $\pm 10$ minutes)	X
	6 hour ( $\pm 20$ minutes)	-
	8 hour ( $\pm 1$ hour)	X (if feasible)
	10 hour ( $\pm 1$ hour)	-
	12 hour ( $\pm 1$ hour)	-
	24 hour ( $\pm 1$ hour)	-
Cycle 2 Day 1	Pre-dose**	X**
Cycle 4 Day 1	Pre-dose**	X
Cycle 6 Day 1	Pre-dose**	X

\* Depending on emerging PK data, the SRC may alter the timepoints for PKs and ECGs. \*\* For the Expansion cohort, this timepoint is needed to be collected, the rest of the time points are not needed. With Sponsor approval the required 10 hour and 12 hour PK sample collections may be omitted, if not feasible.

Meal consumption prior to PK collections will be collected. The last meal consumed prior to dosing on the day of full 24 hour PK collections (Cycle 1) should be recorded.

Additional unscheduled PK samples may be drawn during the study if it is deemed clinically indicated for the patient and/or based on newly emerged data from clinical studies of AC176. Similarly, if any PK timepoint is later deemed unnecessary per acquired clinical PK data, such timepoint may be removed from the PK schedule.

*CONFIDENTIAL*

Study Drug: AC176  
Final Protocol: 10 July 2023 Version 4.0

Sponsor/Development Innovations Study Number: AC176-001/GU 207

Table 9 PK Sampling Timepoints – Intermittent Dosing 7 days On / 7 days Off (28 days per cycle)

	Timepoints relative to AC176 dosing*	ECG* (in triplicate)
Cycle 1 Day 1	Pre-dose	X
	1 hour(±5 minutes)	-
	2 hour(±5 minutes)	X
	3 hour(±10 minutes)	-
	4 hour(±10 minutes)	-
	6 hour(±20 minutes)	-
	8 hour(±1 hour)	X (if feasible)
	10 hour(±1 hour)	-
	12 hour(±1 hour)	-
	24 hour(±1 hour)	-
Cycle 1 Day 8	Pre-dose	X
	1 hour(±5 minutes)	-
	2 hour(±5 minutes)	-
	3 hour(±10 minutes)	-
	4 hour(±10 minutes)	X
	6 hour(±20 minutes)	-
	8 hour(±1 hour)	X (if feasible)
	10 hour(±1 hour)	-
	12 hour(±1 hour)	-
	24 hour(±1 hour)	-
Cycle 2 Day 8	Pre-dose**	X**
Cycle 4 Day 8	Pre-dose**	X
Cycle 6 Day 8	Pre-dose**	X

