\* 7 days on and 7 days off, e.g., C1D1 to C1D7 receive AC176. Dose interrupted C1D8 to C1D14. AC176 dose to continue Cycle 1 on C1D15 to C1D21 and interrupted C1D22 to C1D28. From Cycle 2, the patients will be dosed for 7 days and interrupted 7 days. \*\* For the Expansion cohort, this timepoint is needed to be collected, the rest of the time points are not needed. With Sponsor approval the required 10 hour and 12 hour PK sample collections may be omitted, if not feasible. Meal consumption prior to PK collection will be collected. The last meal consumed prior to dosing on the day of full 24 hour PK collections (Cycle 1) should be recorded. If the sample cannot be collected at the visit as scheduled, it should be collected at the next visit whenever possible.

CONFIDENTIAL

Study Drug: AC176

Sponsor/Development Innovations Study Number: AC176-001/GU 207

Final Protocol: 10 July 2023 Version 4.0

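### On the optional 7-days-on/7-days-off schedule, the second Cycle 1 PK/ECG profile is timed from a Day 8 dose that the dosing calendar does not give, so no scheduled sample falls less than 24 h after a repeat dose

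*Protocol*

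**What the plan says.** The Protocol lets the SRC open alternative schedules, including intermittent ones (Synopsis; Section 5). Each has a PK table in Appendix G and a schedule of assessments in Table 2 or Appendix H.

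For 7 days on and 7 days off:

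- **Sampling.** SOA 5 footnote g.1: "7 days on and 7 days off (Table 9): Pharmacokinetic(PK) sampling will be collected on Cycle 1 Day 1 and 8 pre-dose and post-dose". Table 9 sets out that C1D8 profile under a column timed relative to dosing: a pre-dose sample and nine post-dose samples from 1 to 24 h.
- **Dosing.** The footnote to Table 9, repeated in SOA 5 footnote l.1: "C1D1 to C1D7 receive AC176. Dose interrupted C1D8 to C1D14". Dosing resumes on C1D15 to C1D21.
- **ECGs in g.1.** "triplicate ECGs will also be obtained on Cycle 1 Day 1 and 8 just before the 4-hour and 8-hour post-dose PK blood samples". Table 9 instead puts the C1D1 post-dose ECGs at 2 h and 8 h (8 h if feasible).
- **ECGs in SOA 5 footnote f**, which covers the 7/7, 5/2 and 4/3 schedules: "Additional triplicate ECGs will be performed on Cycle 1 Day 1 and Day 15 just before the 2 hour and 4 hour post-dose" PK samples. SOA 4 footnote f has the same wording.

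Table 3 makes PK after single and multiple doses a secondary objective. The endpoint is given only as PK parameters, with analysis detail left to the SAP (Section 10.4.4).

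**The concern.** A post-dose profile needs a dose. Table 9 asks for one on a day that its own footnote places in the off period. Nothing suggests a deliberate washout design: the column is timed from dosing, and the same footnote asks for the last meal before dosing on the days of full 24 h collection in Cycle 1, which presumes a dose on those days.

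At stake is the only serial repeat-dose profile that the schedule has. Without it, exposure on 7/7 after a week of dosing cannot be compared directly with C1D1, or with the other schedules, at the point where the SRC weighs PK in choosing dose and regimen (Sections 5.1.6 and 10.5.3). Profiles missed while a cohort runs cannot be recovered afterwards.

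**Working it through.** The Protocol gives no figure to reproduce; the check is of calendars and sampling times.

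**1. Second serial profile against dosing days, all eight PK tables.**

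| Schedule (table) | Cycle 1 dosing days | Second profile | On drug? |
|---|---|---|---|
| QD (8), BID (15) | continuous | Day 15 | yes |
| 7/7 (9) | 1-7, 15-21 | Day 8 | **no** |
| 4/3 (10) | 1-4, 8-11, 15-18, 22-25 | Day 4 | yes |
| 5/2 (11) | 1-5, 8-12, 15-19, 22-26 | Day 5 | yes |
| 2 wk/2 wk (12) | 1-14 | Day 8 | yes |
| 2 wk/1 wk (13) | 1-14 | Day 8 | yes |
| 3 wk/1 wk (14) | 1-21 | Day 8 | yes |

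Seven of the eight tables use a dosing day; Table 9 alone does not.

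**2. Where the C1D8 samples fall.** Assume the calendar is followed and doses are taken at the same clock time, as Section 5.1 instructs. Time since dose 7 = 24 h + nominal time. Nominal times 0, 1, 2, 3, 4, 6, 8, 10, 12 and 24 h become 24, 25, 26, 27, 28, 30, 32, 34, 36 and 48 h.

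**3. Count.** After the C1D1 profile, Table 9 schedules 10 samples on C1D8 and one on Day 8 of each of Cycles 2, 4 and 6 (about 24 h after the last dose): 10 + 3 = 13. Number less than 24 h after a repeat dose: 0. In each of the other seven tables the second profile has 8 such samples (1, 2, 3, 4, 6, 8, 10 and 12 h), or 6 if the Sponsor waives the 10 h and 12 h draws (Section 7.7).

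**4. ECGs paired with those samples.** C1D8 pre-dose, 4 h and 8 h become 24, 28 and 32 h after dose 7. The Day 8 ECGs of Cycles 2, 4 and 6 are at about 24 h. None is under 24 h.

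**5. Whether built-in flexibility fills the gap.** A sample that cannot be taken as scheduled moves to the next visit where possible. The next SOA 5 visit is C1D15, which is 8 × 24 = 192 h after the C1D7 dose and is the first dose after seven days off. Even at the longest animal half-life in Section 1.1.1.1 (29 h), the fraction remaining is 0.5^(192/29) ≈ 0.01. A C1D15 profile would be close to a new first dose. Unscheduled samples are permitted but not prescribed.

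**6. What Day 8 samples could recover (illustration only).** A one-compartment oral model with seven daily doses was run with half-lives of 2.6 and 29 h and tmax of 2.6 and 9.7 h (animal ranges, assumed for humans), plus an assumed intermediate half-life of 12 h. The highest Day 8 concentration was about 1% to 72% of the Day 7 peak, and the Day 8 24 h AUC from under 1% to 62% of the Day 7 AUC0-24. In every case the highest Day 8 value was at the first sample. The ratio depends on unknown human kinetics, so Day 8 values do not convert to a repeat-dose peak or AUC without a model.

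**7. Footnote f.** It ties ECGs to C1D15 post-dose PK samples. Cycle 1 PK days are 1 and 8 (Tables 9, 12, 14), 1, 4 and 8 (Table 10), and 1, 5 and 8 (Table 11). C1D15 appears in 0 of the 5 tables that SOA 4 and SOA 5 use, and on 2 weeks on/2 weeks off it is an off-drug day. SOA 3 footnote f names Day 8, which matches Table 13.

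**The case against.** The strongest case is that this is a small matter. 7/7 is one of several optional schedules and needs SRC approval. The PK endpoint is secondary and descriptive, and the DLT and MTD rules do not use this profile. A site would see the clash as soon as it tried to book a post-dose draw on an off day. All of that stands and limits the weight of the point, but Table 9 is a current, ready-to-use schedule and would be wrong on the day it opened.

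Several stronger readings are tempting but unsupported:

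- *That there is no repeat-dose ECG paired with PK at all.* On the calendar there are such ECGs, at about 24, 28 and 32 h after dose 7 and again in Cycles 2, 4 and 6. What is missing is one less than 24 h after a repeat dose.
- *That the Day 8 samples are worthless.* They give a trough and a decline to 48 h, and model-based prediction remains possible.
- *That named endpoints are lost.* The Protocol names only PK parameters, so the loss has to be tied to the multiple-dose objective.
- *That the C1D1 ECG times conflict three ways.* Footnote f calls its ECGs additional and also refers to Appendix G, so its 2 h and 4 h can be read as added to the others. The direct mismatch is 2 h in Table 9 against 4 h in g.1.

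It is also fair that the arithmetic takes the calendar as given. If the calendar is what changes, the 24 to 48 h figures change with it. The example wording before the calendar does not remove the conflict, though: any 7-on/7-off cycle starting on Day 1 has Day 8 off.

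**Conclusion.** The contradiction is explicit, and it appears both in Table 9 with its footnote and in SOA 5 footnotes g.1 and l.1. Taking the dosing calendar and the same clock time each day, 0 of 13 scheduled PK samples after C1D1, and no PK-paired ECG, falls less than 24 h after a repeat dose. Repeat-dose peak and AUC0-24 are not directly observed, and neither the next-visit rule nor discretionary sampling supplies them.

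The reach is narrow: Part A patients on 7/7 (3 to 6 evaluable per dose level, up to 12 with backfill), if the SRC opens it. Part B has no serial profile. A reader might infer that the trial as a whole fails its multiple-dose PK objective. It does not: the other seven tables place the second profile on a dosing day. The off-day pre-dose draws in later cycles are not part of the error either. The other intermittent schedules have them too, and they can be read as end-of-block troughs.

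This should be corrected before the schedule is used. Confidence in the contradiction is high.

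**What to change.** Reconcile Table 9 and SOA 5 footnote g.1 with the Table 9 footnote and footnote l.1, so that the second serial PK/ECG profile falls on a day with a dose. This concerns the sampling day only; dosing is left unchanged. One option under the calendar as written is the last dosing day of the block, C1D7, with the 24 h sample on Day 8. Tables 10 and 11 follow that pattern; for Table 10, g.3 says "pharmacokinetic (PK) sampling will be collected on Cycle 1 Day 1 and 4 pre-dose and post-dose at" the listed times, Day 4 being the last of four dosing days.

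In the same edit:

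- State one C1D1 post-dose ECG time where Table 9 (2 h) and g.1 (4 h) differ.
- Make footnote f of SOA 5 and SOA 4 schedule-specific, or have it refer only to Appendix G. SOA 5 footnote f should not name one day for all three of its schedules: Day 7 is off drug on 5/2 ("Dose interrupted C1D6 to C1D7") and on 4/3 ("Dose interrupted C1D5 to C1D7").
- Optionally, label the Day 8 samples of Cycles 2, 4 and 6 by time since last dose.

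Cost: a small protocol amendment with the usual review. On the last-dosing-day option there are the same 10 samples over the same number of visit days (Days 7 and 8 instead of 8 and 9), and Day 8 already has a CBC in SOA 5.

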Patients dosing schedule may include:
  - 1) 2 weeks on 2 weeks off, e.g., C1D1 to C1D14 receive AC176. Dose is interrupted C1D15 to C1D28. AC176 dose to continue C2D1 to C2D14. Dose is interrupted C2D15 to C2D28, etc.
  - 2) 3 weeks on 1 week off, e.g., C1D1 to C1D21 receive AC176. Dose is interrupted C1D22 to C1D28. AC176 dose to continue C2D1 to C2D21. Dose is interrupted C2D22 to C2D28, etc.

Patients will be instructed to take one dose of AC176 at the same time every day immediately after a meal. The patients will be asked to take AC176 in the morning immediately after a meal, and other concomitant medications in the evening; or at least 4 hours apart from taking AC176, if possible.

Study drug compliance will be assessed at each patient visit by review of the dosing diary.

- m Prostate-specific antigen (PSA) blood samples will be taken prior to dosing Cycle 1 Day 1 (unless collected within the previous 72 hours), and at Day 1 of every cycle, and at the EOT visit if not taken in the previous 4 weeks, and at progression. Additional PSA assessments after the 30-day safety follow-up visit will be performed as on treatment until PD or another withdrawal criterion is met.
- n CT/MRI scans of the chest, abdomen and pelvis should be taken  $\leq$  4 weeks prior to initiation of treatment. CT/MRI scans of the chest, abdomen, and pelvis should be taken every 2 cycles (8 weeks)  $\pm$  5 days up to 24 weeks, then every 12 weeks  $\pm$  5 days, and at the End of Study visit (if scans were not taken in the previous 8 weeks) and, if clinically indicated, imaging of any other known or suspected sites of disease (e.g., brain). Lymph nodes should be evaluated using PCWG3 criteria and not RECIST v1.1.
- o Bone scans - technetium only -  $\leq$  4 weeks prior to initiation of treatment, every 2 cycles (8 weeks)  $\pm$  5 days up to 6 cycles (24 weeks), then every 3 cycles (12 weeks)  $\pm$  5 days, and at the End of Study visit if scans were not taken in the previous 8 weeks. Bone lesions should be evaluated using PCWG3 criteria and not RECIST v1.1.
- p An EOT visit should be performed for all patients who permanently discontinue study treatment. If the decision to permanently discontinue treatment is made at a scheduled visit, the EOT visit should be performed instead of the scheduled visit (preferably within 7 days and no later than 14 days after the last treatment).

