- q All patients will be followed during the off-treatment period until all treatment-related toxicity resolves, or for at least 30 days post-study drug discontinuation, or until the start of another anti-cancer treatment. Any concomitant medications received up to 30 days after the last dose of study medication should be recorded.
- r Follow-up for PD visits for tumor assessment by imaging (CT scan/MRI/bone scan, if applicable) for patients who discontinue study treatment without having PD based on RECIST v1.1 (see [Appendix B](#)) should be performed as on treatment until PD or another withdrawal criterion is met (see Section [7.5.3](#)). At these visits, serious adverse events (SAEs) occurring during the study that are considered to be related to study treatment or procedures will be followed until resolution.

*CONFIDENTIAL*

Study Drug: AC176

Sponsor/Development Innovations Study Number: AC176-001/GU 207

Final Protocol: 10 July 2023 Version 4.0

**Table 18 SOA 5 (GU 207 Schedule of Assessments) - Intermittent Dosing with 7, 5, or 4 Days on Followed by 7, 2, or 3 Days Off, Respectively, 28 Day Cycle**

	Dose-Escalation, Backfill and Expansion Cohorts AC176 Monotherapy Treatment Period (1 Cycle =28 days)					EOT t	30-Day Safety FU u	FU for PD v
	Cycle		C1	C2	C3+			
Treatment day	1	8	15 ( $\pm 2$ )	1 ( $\pm 2$ )	1 ( $\pm 2$ )		$\pm 5$ days	$\pm 5$ days
Written ICF for main study	See Table 1 for pre-screening/screening procedures a							
Physical examination and weight b	X		X	X	X	X	X	
Safety laboratory (hematology, [including PT/PTT/(INR or aPTT)], immature platelet function, biochemistry, urinalysis) c,d	X		X	X	X	X	X	
Vital signs d	X		X	X	X	X	X	
CBC only d		X						
Concomitant therapy				X				
ECOG performance status c	X		X	X	X	X	X	
12-lead electrocardiograms (triplicate) h,i			X	X	X e	X e		
Adverse events (AEs)/Serious adverse events (SAEs)				X				
Pharmacokinetics j	See Appendix G: Table 9, Table 10 or Table 11							
(Optional) Tumor biopsy m				X (+ 5 days)				
Blood sampling for biomarkers (ctDNA) n	X (pre-dose)			X	C5 & C8 only	X		
ARv7 blood sample o (CTC)	X (pre-dose)					X		
AC176 dosing	See footnote l							
Review patient diary p			X	X	X	X		
PSA q	X (pre-dose)			X	X	X		X q

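### The intermittent schedules keep the continuous-dosing laboratory days, so most chemistry and full hematology panels fall at the end of the drug-free break and laboratory safety is biased in favour of intermittent dosing

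*Protocol*

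**What the plan says.** The schedules of assessments for intermittent dosing are Table 16 (SOA 3: 2 weeks on/1 off, 21-day cycle), Table 17 (SOA 4: 3 weeks on/1 off or 2 weeks on/2 off) and Table 18 (SOA 5: 7/7, 5/2 and 4/3 days). In Tables 17 and 18 the panel row reads "Safety laboratory (hematology, [including PT/PTT/(INR or aPTT)], immature platelet function, biochemistry, urinalysis"; Table 16 has an equivalent row. In all three it is marked at C1D1, C1D15 (±2 days), Day 1 (±2 days) of Cycle 2 and later cycles, end of treatment and the 30-day follow-up. C1D8 has a blood count only. Table 2 uses the same days for once- and twice-daily dosing.

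The dosing days are in footnote l of SOA 4 and SOA 5, and in the dosing row of Table 16:

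- 7/7: "Dose interrupted C1D8 to C1D14. AC176 dose to continue Cycle 1 on C1D15 to C1D21 and interrupted C1D22 to C1D28".
- 5/2: "C1D1 to C1D5 receive AC176. Dose interrupted C1D6 to C1D7", repeated weekly.
- 4/3: "C1D1 to C1D4 receive AC176. Dose interrupted C1D5 to C1D7", repeated weekly.
- 2 weeks on/2 off: "C1D1 to C1D14 receive AC176. Dose is interrupted C1D15 to C1D28".
- 3 weeks on/1 off: "C1D1 to C1D21 receive AC176. Dose is interrupted C1D22 to C1D28".
- 2 weeks on/1 off: dosing on Days 1-14 of a 21-day cycle.

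The pharmacokinetic days, by contrast, were set separately for each schedule. For 7/7, SOA 5 footnote g says "On Cycle 2 Day 8, Cycle 4 Day 8, and Cycle 6 Day 8, a pre-dose PK sample will be collected from all patients", the day after an on-block ends.

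**The concern.** Dose-limiting toxicities and clinical chemistry/hematology are primary endpoint variables (Section 2, Table 3). Under Section 5.1.3 a Grade 3 liver-test abnormality or a Grade 4 platelet decrease counts as a DLT whatever its duration, so one abnormal value decides. If blood is drawn only after drug-free days, an abnormality that arises on drug and recovers in the break leaves no scheduled record. Tables 5 and 6 provide for Grade 3/4 events that resolve within 7 days, which is the length of the 7/7 break.

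In the 3+3 rule of Table 4, one missed event turns 1 of 3 (add three patients) into 0 of 3 (escalate). Alternative schedules may run concurrently (Section 5), and the Sponsor and SRC choose the dose and schedule for Part B (Section 5.1.7). A gap that grows with the length of the break makes intermittent cohorts look cleaner than once-daily cohorts for reasons unrelated to the drug. Uncollected samples cannot be recovered at analysis.

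**Working it through.** The plan gives no figure to reproduce, so the check sets the two calendars against each other.

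**Inputs.** Dosing days and laboratory days are those listed above. I assume the draw precedes that day's dose. The schedules say only that vital signs come before blood work and dosing, so this is likely but not stated.

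**Formula.** Gap = visit day minus the latest dosing day before it. Day 1 of the next cycle is Day 29 (28-day cycle) or Day 22 (21-day cycle).

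**Count.** Post-baseline panels from C1D15 through C6D1 number six (C1D15 and Day 1 of Cycles 2 to 6). The last column counts those with a gap of at most 1 day.

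| Schedule | Dosing days in the cycle | C1D8 count | C1D15 panel | Next Day 1 panel | Panels within 1 day |
|---|---|---|---|---|---|
| Once daily | 1-28 | 8-7 = 1 | 15-14 = 1 | 29-28 = 1 | 6 of 6 |
| 7/7 | 1-7, 15-21 | 8-7 = 1 | 15-7 = 8 | 29-21 = 8 | 0 of 6 |
| 5/2 | 1-5, 8-12, 15-19, 22-26 | 8-5 = 3 | 15-12 = 3 | 29-26 = 3 | 0 of 6 |
| 4/3 | 1-4, 8-11, 15-18, 22-25 | 8-4 = 4 | 15-11 = 4 | 29-25 = 4 | 0 of 6 |
| 3 wk on/1 off | 1-21 | 8-7 = 1 | 15-14 = 1 | 29-21 = 8 | 1 of 6 |
| 2 wk on/2 off | 1-14 | 8-7 = 1 | 15-14 = 1 | 29-14 = 15 | 1 of 6 |
| 2 wk on/1 off | 1-14 (of 21) | 8-7 = 1 | 15-14 = 1 | 22-14 = 8 | 1 of 6 |

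**Visit window.** On 7/7 a panel drawn 2 days early falls 6 days after the last dose. One drawn 2 days late falls 1 day after a dose, but only two doses into the new block. Neither edge samples the end of an on-block.

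**Reading.** Three of the six intermittent schedules (7/7, 5/2, 4/3) have no nominal on-treatment panel within 1 day of a dose. The other three have one, at C1D15 inside the DLT window, and none from Cycle 2. On 7/7 the C1D8 count is close to drug but covers counts only, after the first on-block only. On 5/2 and 4/3 even that count follows the break, although the break is just 2 or 3 days.

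**The case against.** Several points on the other side stand:

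- Intermittent schedules are optional and need SRC approval. Section 10.5.3 lets the timing of safety evaluations be revised in consultation with the SRC. Adverse events are recorded throughout, and Appendix F asks the investigator to stay alert to liver biochemistry. These soften the gap, but none of them schedules a panel.
- The DLT consequence is narrow. Grade 4 neutropenia counts only if it lasts more than 7 days. Asymptomatic Grade 3 or higher electrolyte changes count only beyond 72 hours. Other Grade 3 non-hepatic laboratory values count only with clinical manifestations leading to intervention or hospitalization. On 7/7 the C1D8 count covers platelets after the first on-block. The exposed criterion is mainly Grade 3 liver tests on 7/7 in Cycle 1.
- Tables 5 and 6 are conditional. They say what to do if an event resolves within 7 days, not that it will.

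A reader might also infer more than the documents support:

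- **That Cycle 1 is blind on every intermittent schedule.** It is not: on 3 weeks on/1 off, 2 weeks on/2 off and 2 weeks on/1 off, the C1D15 panel is on drug or one day after the last dose.
- **That toxicity goes unseen.** The C1D8 count, the ±2-day window, adverse-event recording and unscheduled tests may each catch an event.
- **That schedules cannot be compared.** No formal comparison is planned, safety summaries are by dose level (Section 10.4.3), and clinical adverse events do not depend on the laboratory calendar. The bias is in the laboratory comparison.
- **That toxicity has gone because the drug has washed out.** The protocol gives only animal half-lives (2.6 to 29 hours, Section 1.1.1.1) and no recovery kinetics. Residual drug is not a measure of recovery.

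**Conclusion.** The point holds in this form. At nominal visit days, every on-treatment chemistry and full hematology panel on 7/7, 5/2 and 4/3 falls at the end of the break. From Cycle 2 the same is true of all six intermittent schedules, with gaps of 3 to 15 days against at most 1 day on once-daily dosing. Transient laboratory toxicity may go undetected, and the error favours intermittent over continuous dosing. It matters most for liver tests on 7/7 in Cycle 1, where no chemistry is scheduled on or just after drug inside the DLT window, and least on 5/2 and 4/3, where recovery within 2 or 3 days is uncertain.

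The conclusion assumes pre-dose draws at nominal days and some toxicity that recovers during a break. How often that happens cannot be estimated from the protocol, so no probability of a missed event is offered. The change should be made before an intermittent cohort opens.

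**What to change.** Reconcile the laboratory calendar in Tables 16-18 with the dosing calendars. Add hematology and biochemistry to visits that already draw blood at or just after the on-period:

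- **7/7:** C1D8 (already a blood-count visit) and Day 8 of Cycles 2, 4 and 6.
- **2 weeks on/2 off and 2 weeks on/1 off:** Day 15 of Cycles 2, 4 and 6.
- **3 weeks on/1 off:** Day 22 of Cycles 2, 4 and 6. For Part B, first settle whether Cycles 4 and 6 are visits: Table 14 marks only Cycle 2 for expansion patients, while SOA 4 footnote h lists all three.
- **4/3 and 5/2:** the Part A pharmacokinetic visit at C1D4 or C1D5, and Day 5 or Day 6 of Cycles 2, 4 and 6 where these take place (Tables 10 and 11 make them subject to feasibility).

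Keep the Day 1 draws. When laboratory worst grade is tabulated by schedule, show days since last dose. Nothing here changes a dose, a hold or a stopping rule.

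The cost is an amendment to the schedules and three or four extra local panels per patient through Cycle 6. More laboratory abnormalities will be recorded on intermittent schedules.

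The repair is partial. On 7/7 there are 6 × 2 = 12 on-blocks through Cycle 6 and it samples four; the second Cycle 1 block, inside the DLT window, is not among them. Odd-numbered cycles after the first, and Cycle 1 for Part B patients on 4/3 and 5/2, also stay unsampled near drug unless a visit is added.
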